2.1 Trial Design

A single-centre, unblinded, parallel-group, superiority randomised controlled trial with 1:1 allocation, alongside a mixed-methods process evaluation.

LAs that are randomised to the control arm of the trial will be provided with intervention materials at the end of the study.

2.2 Study Setting

English Local Authorities.

2.3 Eligibility criteria

We will recruit LAs, one key informant per LA and ~15 workshop participants per intervention LA.

All LAs in England will be eligible, although we will begin with inviting LAs based in the most deprived 40% of England. If we are unable to meet the recruitment target with these invites, we will then extend recruitment to 50%, 60% and so on until we meet the recruitment target of 60 LAs. LAs with existing food strategies (or similar) or who are members of e.g., Health Determinants Research Collaborations will be included as these may represent those with greatest motivation to progress, as well as those who have already made good progress. Randomisation will help ensure these characteristics are evenly distributed. We will exclude non-English localities to provide a reasonably consistent policy context.

Individuals will be eligible to be key informants if they (a) work at a participating LA, and (b) have a core responsibility for food etc. All key informants will be eligible to take part in the study.

Workshop participants will be local decision makers in any sector with the power to enact workshop insights and representatives of local community food organisations, all workshop participants will be eligible to take part in the study.

2.4 Recruitment

We will identify the 40% most deprived LAs in England and their Directors of Public Health with help from our third-sector collaborator the Association of Directors of Public Health (ADPH). ADPH work with selected LAs across England in Health Determinants Research Collaborations (HDRC), and their website has an LA directory with current Directors of Public Health (DPH). Any LAs missing a DPH in the directory will be located through internet searches. Each LA's key informant (LAKI) (one for each LA, n=60) will be recruited as we recruit the LA.

We will work with LAs to recruit approx. 15 stakeholder participants to attend a one-day intervention workshop in each intervention LA. Within boundaries of our inclusion criteria, we will encourage key informants to think broadly in terms of diversity (i.e., gender, ethnicity, sector and career stage) when selecting workshop participants.

As this intervention is targeted at professional stakeholders, we have not conducted and will not conduct any specific PPI activities. We did seek feedback from public health professionals (via the Association of Directors of Public Health) on the idea for the work as it was being developed who confirmed that DHI are a high priority and the intervention would be attractive. Further, we will include one or two representatives of local community food organisations to bring the voice of those with experience of DHI in each workshop. To ensure wide participant recruitment, we will provide LA key informants with example roles (e.g., school catering manager).

2.5 Randomised Control Trial Data collection

2.5.1 Local authority level baseline and 12-month data collection for primary outcome

Based on the logic model described in Figure 2, data will be collected from each LA on the primary outcome at baseline and 12 months to document existing policies related to dietary inequalities prior to randomisation and intervention implementation. These data provide a reference point for assessing change at the 12-month follow-up interview. A structured interview guide will be used with a checklist of questions (**Table 1**) to identify policies. All interviews will be recorded on Microsoft Teams. Interviews will be conducted by a member of the research team with the LAKI. The interview recording and generated transcription will be stored until the data capture form has been completed and will then be deleted.

Table 1. Key Informant interview guide for baseline data collection

| Variable | Interview guide |
|----------------------------------|--|
| Date | 1. Date of data collection |
| LA and KI information | 
 1. Name of LA 2. What role does the Key Informant have 3. How long as the Key informant been in their current role? 4. How long has the Key Informant been in a role relevant to dietary inequalities |
| Current food strategies | 
 1. Does the LA have a current Food Strategy (Y/N) 2. Is the LA part of a local food partnership (Y/N) 3. Is the LA a member of the Health Determinants Research Collaboration (Y/N) |
| Current policies for DHI (known) | 1. Can you tell me what policies have been put in place in the last 12 months or will be put in place in the next 12 months to address dietary inequalities (defined as any intentional actions explicitly aiming to address dietary inequalities)? Use relevant prompts with examples from the Food System Transformation Solution Bank |

| | |
|--|---|
| | 
 2. For each policy: what was (or will be) the date of implementation? 3. For each policy: please tell me more about that, what it involves etc Is there anything else that's relevant for this policy? (for each response on a particular policy, ask again about details and repeat until data saturation is achieved for that policy). 4. Are there any other policies in place to address dietary inequalities? Repeat the above questions (i.e., 2-4) for each policy until all policies known to the Key Informant are given. |
|--|---|

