1.2 The Intervention

The intervention was co-developed by MW, KP and AS with Jersey’s public health team, then refined and delivered in Guernsey. The Association of Directors of Public Health confirm DHI are a high priority, and the intervention would be attractive.

The intervention will be flexible to local context, is described using the Template for Intervention Description and Replication, (11) is supported by a Theory of Change (**Figure 1**), will be delivered by the research team and comprise:

- 1 or more online 2-hour pre-meet with the key informant (defined below; and relevant team members) ~3 months pre-workshop to review roles, agree upon a focus, and identify workshop participants. Workshop participants (n~15) will be local decision makers in any sector with the power to enact workshop insights (12) and representatives of local community food organisations to bring the voice of those with experience of DHI. Conducting GMB in one day is ambitious but necessary to maintain engagement. Focusing on one locally-agreed population or outcome (e.g.

children, vegetable intake) makes one-day manageable and the intervention flexible to local context. Follow-up meetings will be conducted as required.

- intelligence website circulated to workshop participants summarising local data on DHI to provide context. To be developed by Food Foundation from routinely available data (<https://fingertips.phe.org.uk/>) and their regular food security surveys. Including e.g. local prevalence of children in poverty not eligible for free school meals, type 2 diabetes and food insecurity.
- one-day in-person GMB workshop, developing a CLD and using this to identify potential solutions. Guided by manuals and scripts. Facilitated by 2-3 researchers.
- Around three online 1-2 hour post-meets with key informants (and team) 1 week, 1 month and 3 months post-workshop to refine the CLD, identify further solutions, and support solution prioritisation. Informed by our comprehensive database of Food System Transformation Solutions enabling sharing of best practice.(13)

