1.4 Primary & Secondary outcomes

1.4.1 Primary outcomes

Number of policies planned or implemented within the last 12 months that explicitly aim to reduce DHI

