4.1 Data storage

Data will be handled and stored in line with IMS Epidemiology data management policies for all quantitative data collected.

For interviews recorded on Microsoft Teams, the data will initially be captured as a video/audio mp.4 file. This recording will automatically save into OneDrive on the University's Microsoft's 365 platform which the study researcher has access to using their RAVEN credentials. The Microsoft Teams functionality for transcription will also be used during the interview. Following the interview, a transcript will be available in Teams and will be downloaded into OneDrive as a Word document. Following the interview, the video/audio mp.4 file will be converted to an audio only mp.3 file, using the software VLC. The audio only mp.3 file and transcript Word document, will then be saved into the IMS Epidemiology Unit's Secure Research Drive (SRD), a separate server which requires two factor security authentications to access. Once safely transferred to the SRD, all files will be deleted from Microsoft Teams and OneDrive.

All recordings and transcripts will be saved on the SRD using the study name, LA name and the date/time of the interview. Transcriptions will be anonymised. Audio recordings will be destroyed once transcriptions have been checked. Anonymous transcripts will be kept separately from identifying information, which will be retained for administration purposes until coding has been completed and then destroyed.

Due to the nature of the research topics, the research team is confident that the content of the interview data will fall within Level 2 or lower under the 'University data security classifications and guidelines', which is a requirement for data storage on the public cloud service when using Microsoft Teams.

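### The primary outcome is an unverified count of the policies one unblinded key informant can name, so awareness that rises after randomisation in the intervention arm alone would inflate the estimated effect.

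*Protocol*

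**What the plan says.** Protocol section 1.4.1 defines the primary outcome as "Number of policies planned or implemented within the last 12 months that explicitly aim to reduce DHI". Section 2.3 sets one source per LA: "We will recruit LAs, one key informant per LA and ~15 workshop participants per intervention LA". Food must be a core part of the informant's job.

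Section 2.5.1 describes the measurement, at baseline (before randomisation) and at 12 months: "Interviews will be conducted by a member of the research team with the LAKI". Table 1 asks about actions put in place in the past 12 months or due in the coming 12, asks for an implementation date for each, and continues "until all policies known to the Key Informant are given". For prompting it instructs: "Use relevant prompts with examples from the Food System Transformation Solution Bank".

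Section 1.2 has the research team deliver the intervention and involves the key informant directly, in the pre-meets and in about three post-meets. The post-meets are described as "Informed by our comprehensive database of Food System Transformation Solutions enabling sharing of best practice". Sections 2.1 and 3.2 make the trial open label. Section 3.3 analyses the count by linear regression adjusted for baseline. It scopes strategy documents and policy submissions only as context for the qualitative work.

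On source material, section 2.5.1 says the recording and transcription "will be stored until the data capture form has been completed and will then be deleted". Section 4.1, on interviews recorded in Teams, says "Anonymous transcripts will be kept separately from identifying information".

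**The concern.** The outcome is what the informant knows and chooses to name, not what has been verified. The protocol expects the intervention to change that knowledge. Understanding and collaboration are secondary outcomes, compared between arms in key informants, and section 2.8.2 lists shared understanding among the theorised mechanisms. Under section 2.7, control informants give about two hours, for data collection only.

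An intervention informant may therefore reach the 12-month interview aware of more recent or planned activity elsewhere in the LA, or readier to describe an activity as aimed at dietary health inequalities. That would raise the count without any policy having changed, and in the direction of the hypothesis. The trial could not then separate more policies from more policies reported. With no masking stated, and with the transcript deleted under section 2.5.1, nobody could later recode the count masked to arm.

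**Working it through.** **Inputs.** From section 3.1: 30 LAs per arm, a target difference of two policies, SD 3 or SD 2, and stated power of 72% and 97%. The protocol does not state the significance level; two-sided 5% is assumed because it reproduces the stated power. The reporting shift *b* (extra policies named per intervention LA with no true effect) is not in the protocol, so a range is shown.

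**Step 1: the plan's own figures.** Two-sample t test with 58 degrees of freedom and SE = SD × √(2/30):
- SD 3: SE = 3 × 0.258 = 0.775; noncentrality 2/0.775 = 2.58; power 71.9%.
- SD 2: SE = 2 × 0.258 = 0.516; noncentrality 2/0.516 = 3.87; power 96.8%.

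Both round to the stated 72% and 97%.

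**Step 2: smallest significant difference.** This is t(0.975, 58) × SE = 2.00 × SE, or about 1.55 policies (SD 3) and 1.03 policies (SD 2).

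**Step 3: reporting shift with no true effect.** The noncentrality is *b*/SE. The probability of a significant result favouring the intervention is P(T > 2.00), with T noncentral t on 58 degrees of freedom and no baseline correlation:

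| Shift *b* (assumed) | SD 3 | SD 2 |
|---|---|---|
| 0 | 2.5% | 2.5% |
| 0.5 | 9.3% | 15.7% |
| 1 | 24.5% | 47.8% |
| 1.5 | 47.8% | 81.5% |
| 2 | 71.9% | 96.8% |

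**Step 4: does baseline adjustment help?** With an assumed baseline correlation of 0.5, the residual SD is SD × √(1 − 0.25) = 0.866 × SD. A shift of one policy then gives 31.1% (SD 3) or 59.4% (SD 2). Adjustment narrows the standard error but leaves a shift that arises after randomisation in place, so the false-positive probability goes up.

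**Step 5: the two retention rules.** Section 2.5.1 deletes both recording and transcription when the data capture form is done. Section 4.1 destroys the audio once transcripts have been checked and keeps anonymised transcripts. Section 4.1 covers these same Teams interviews; the process-evaluation material is handled separately in section 4.2. The two rules cannot both be followed.

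**The case against.** Much can be said for the plan. Baseline is measured before randomisation and adjusted for, which deals with stable differences between informants. One guide for all LAs makes the prompting symmetric, and examples may help an unprimed control informant more, which would narrow a gap. The 12-month window and the implementation dates limit what can be added: discovering an older policy should not raise the count. Informants with food as a core responsibility will miss less.

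These points stand, but they limit the problem without removing it. None deals with awareness or labelling that changes in one arm after randomisation, for policies inside the window or still planned. The follow-up question in Table 1 about other policies does not restate the window, and no counting rule is written down.

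A reader might infer more than the text supports:
- *That the workshop facilitator interviews the same LA.* The protocol says only that both roles come from the research team. It neither states nor excludes overlap.
- *That intervention informants have rehearsed the prompts.* The post-meets are only informed by the database, and the last scheduled one is three months after the workshop. Table 1 is titled for baseline; its use at 12 months is inferred from the section heading and text.
- *That prompting control informants at baseline adds to the bias.* Any such exposure would push towards no difference.
- *That a masked count is impossible.* That follows only from section 2.5.1, and only once the form is complete.
- *That the bias is shown to exist.* It is not. The table shows what an assumed shift would do.

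**Conclusion.** The concern holds as a risk of differential reporting in an unmasked, single-source, unverified primary outcome. Its direction favours the intervention; its size is unknown. Across assumed shifts of 0.5 to 1.5 policies, the chance of a false positive favouring the intervention is about 9% to 48% (SD 3) or 16% to 82% (SD 2), against 2.5%. These figures assume no true effect, 30 LAs per arm, a two-sided 5% test and no baseline correlation. A shift equal to the trial's own target of two policies would reproduce the planned power exactly.

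A plan genuinely adopted because of the workshop is a true effect on the outcome as defined. The bias concerns only policies named or labelled differently. The contradiction between sections 2.5.1 and 4.1 is a matter of text and needs no assumption.

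**What to change.** 1. Reconcile sections 2.5.1 and 4.1 so that de-identified transcripts are kept until the primary outcome is locked. Do this before baseline interviews begin; recruitment is expected to start in April 2026.
2. Have an existing team member who did not deliver in that LA count the policies, masked to arm, from transcripts stripped of workshop references. Use a written counting rule that applies the 12-month window through the implementation dates already collected.
3. Replace the Solution Bank examples with one neutral list of policy domains, sent to both arms before each interview. Ask for the dated document behind each named policy where one exists.
4. Where the rota allows, use a 12-month interviewer who did not facilitate that LA's workshop.
5. Report implemented and planned policies separately as a supporting analysis.

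The cost is protocol wording, some redaction and document-checking time, and rota planning. The protocol does not give the team's size, so the sponsor must confirm that items 2 and 4 can be staffed from within it. Section 4.2 already allows non-identifiable data to be kept.

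Masking will be imperfect. Items 2 and 4 reduce interviewer and coder bias only, because extra policies the informant names are already in the transcript. Item 3 and the dating rule are what address informant awareness. The residual reporting bias should be stated as a limitation.

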3.1 Sample Size for quantitative analyses

We will recruit 60 LAs: 30 each in the intervention and control arms. We will recruit one key informant per LA (n=60). We aim to recruit all workshop participants (n≈450). Given novelty, we do not have robust data to inform sample size calculations. Instead, we used best practice guidance on pilot studies suggesting ~25-35 per arm to

detect small effect sizes with 90% power. (18) A sample size of 60 has 72% power to detect a difference of two policies if the standard deviation is 3, and 97% if it is 2.

We will use baseline data to re-estimate the sample size required to detect a difference of two policies with 90% power. (19) If this is ≤ 60 , we will consider the study adequately powered. If it is >60 , we will consider it underpowered and disseminate as a pilot study. Our data will be made available for others (or us) to add to in the future.

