3.2 Randomisation & Enrolment

Trial LAs will be unblinded (open label) and randomised using a computer-generated randomization list with a 1:1 ratio. Specifically, our study statistician will generate the randomisation list using Stata statistical software. Stata makes use of a computer system clock as the seed point, which produces a pseudo-random list generally regarded as acceptable for RCTs.

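### The primary outcome counts policies defined as any intentional action, with no rule for whether a multi-action programme scores one or several

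*Protocol*

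**What the plan says.** Protocol section 1.4.1 gives the primary outcome as "Number of policies planned or implemented within the last 12 months that explicitly aim to reduce DHI". Section 3.1 sets the target difference at two policies, and section 3.3 compares mean counts by linear regression adjusted for baseline.

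The unit is defined only in a parenthesis in the Table 1 interview question (section 2.5.1): "defined as any intentional actions explicitly aiming to address dietary inequalities". For each policy named, the guide asks the date, what it involves and whether anything else is relevant to that policy. It then moves on: "Repeat the above questions (i.e., 2-4) for each policy until all policies known to the Key Informant are given". A separate row of Table 1 records, yes or no, whether the LA has a food strategy.

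On collection, section 2.5.1 says: "Interviews will be conducted by a member of the research team with the LAKI". There is one key informant per LA, section 3.2 states that the trial is open label, and no masked scoring is described. Under section 1.2, intervention informants attend meetings after the workshop to "refine the CLD, identify further solutions, and support solution prioritisation". That section plans around three of these meetings; the synopsis gives one.

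Section 3.1 also makes the baseline count decide how the trial is classed: "We will use baseline data to re-estimate the sample size required to detect a difference of two policies with 90% power". At 60 LAs or fewer the trial is treated as adequately powered, and above 60 as a pilot.

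**The concern.** A count needs a rule for what is one unit. Suppose an LA runs a holiday food programme made up of three actions, each aimed at dietary inequalities. One informant may name the programme (score 1) and another may name the three actions (score 3). Both answers fit the definition in Table 1.

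If this varied equally in both arms it would add noise. It may not be equal. Intervention informants have worked through a list of solutions and ranked them, which could make them report the same activity in smaller pieces at 12 months. The interviewer belongs to the research team and may know the arm. The primary analysis is a difference in mean counts, so each extra item listed in one arm adds directly to the estimate. Adjusting for baseline cannot correct a reporting habit acquired after randomisation.

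**Working it through.** **1. The plan's own figures.** Inputs from section 3.1: 30 LAs per arm, difference 2, SD 3 or 2. Alpha is not stated there; two-sided 5% is assumed. Two-sample t-test, noncentrality = 2 / (SD × √(2/30)), 58 degrees of freedom:

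| SD | Power, noncentral t | Power, normal approximation | Stated |
|---|---|---|---|
| 3 | 71.9% | 73.3% | 72% |
| 2 | 96.8% | 97.2% | 97% |

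The stated figures reproduce.

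**2. Inflation from itemising.** Let both arms have the same true policy activity. A share q of intervention LAs report one plan as m items, and no control LA does. The expected difference in means is then q × (m − 1). The protocol gives neither q nor m, so both are assumptions:

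- q = 0.25, m = 3: 0.25 × 2 = 0.5, a quarter of the target difference.
- q = 0.5, m = 3: 0.5 × 2 = 1.0, half of it.
- q = 0.5, m = 5: 0.5 × 4 = 2.0, all of it.

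**3. Chance of a false result favouring the intervention.** Simulated trials with no true effect, 30 v 30, unadjusted two-sided 5% t-test. Counts are Poisson with mean 4 (SD 2) or mean 9 (SD 3), to match the protocol's two SDs. The nominal rate in this direction is 2.5%.

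| q | m | SD 2 | SD 3 |
|---|---|---|---|
| 0.25 | 3 | 15% | 9% |
| 0.5 | 3 | 44% | 23% |
| 0.5 | 5 | 87% | 64% |

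**4. A second model.** Let a share of all intervention-arm policies be scored as two, with mean count 6 and SD 3 (assumed). At 10% the difference is 6 × 0.10 = 0.6 and the false-positive rate is 10.7%. At 25% the difference is 1.5 and the rate is 37%. Mild splitting thus gives a similar answer under either model.

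**5. Baseline adjustment.** The simulations are unadjusted. Adjustment would improve precision, but the expected inflation would remain, because the baseline count is taken before randomisation and cannot reflect itemising that starts afterwards.

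**The case against.** Much can be said for the protocol here.

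- A reader might infer two rival units, policies in section 1.4.1 and actions in Table 1. The text does not support that. The parenthesis is the protocol's own and only definition of a policy, and nothing in section 1.4.1 says a multi-action programme scores 1. The gap is a missing counting rule.
- Table 1 gives a food strategy its own row, and its detail questions are tied to the policy just named; only the last question asks for other policies. This suggests that components belong with their parent. It is a hint, not a rule, and the definition still lets each component qualify if the informant names it separately.
- The interviewer's prompts from the Solution Bank are not restricted by arm, so control informants also hear solution-level examples. This narrows any difference between arms. It does not match the intervention arm's experience of listing and ranking its own solutions.
- New solutions that become planned actions are the intended effect and should count. The concern is only with existing or single plans reported in pieces.
- A reader might also infer that counting actions would push the section 3.1 re-estimate well above 60 and turn the trial into a pilot. That follows only if the SD is rescaled to actions while the target stays at two. With policies at mean 4 and SD 2, and 1.5 or 2 actions per policy, the SD becomes 3.32 or 4.47. Two policies then equal 3 or 4 actions, and the required total is about 54 or 56, still within 60.
- A statistical analysis plan or data capture form, not seen here, may hold a rule. The protocol nonetheless defines the unit itself, in the instrument used before randomisation.

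**Conclusion.** The point holds as a weakness in how the primary outcome is counted. The definition lets a programme and its components each qualify, no rule settles how they count, and the open-label, single-informant interview leaves room for the arms to itemise differently. That this could bias the result upward is plausible but not shown. Its size is unknown, because it depends on q and m, which the protocol does not give. Under the mildest assumption tabulated in step 3 (a quarter of intervention LAs listing one plan as three items, no control LA doing so), the inflation is 0.5 policies and the false-positive rate in favour of the intervention is about 9–15% instead of 2.5%. The higher figures need half of intervention LAs to split a plan and should be read as the upper end of an illustration.

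The documents do not show contradictory outcomes or an error in the sample size. The stated power figures need no change. This is a cheap improvement to a primary outcome, best made before baseline interviews begin.

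**What to change.** Keep the broad definition, so that stand-alone actions still count. Add a nesting rule to Table 1 and a parent-entry field to the data capture form: an action that is a component of a named programme or strategy is recorded beneath it, and the group counts once.

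Apply the same rule at baseline and 12 months. Have an existing team member score both from forms with LA name and arm removed. Do this before the source is deleted: section 2.5.1 deletes the recording and transcription once the form is complete, while section 4.1 describes keeping anonymised transcripts. Masked scoring cannot undo what the informant chose to list, but with the nesting field it can regroup the items.

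Use the nested count for the primary analysis and for the section 3.1 re-estimation, and state that the target of two is in that unit. Report the un-nested action count as a sensitivity analysis; a large gap between the two results would show how far the effect depends on itemising.

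The cost is some wording, one form field and scoring time, with slightly lower counts. No extra LAs or visits are needed. Section 2.7 expects recruitment to start in April 2026, so the wording should be settled before then.
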